#### 7.1.2 Clinical Procedures/Assessments

## 7.1.2.1 Urinary Albumin: Creatinine Ratio (ACR)

A urine sample will be collected on site at the times listed in the Trial Flow Chart – Section 6.0 for measurement of the urinary albumin:creatinine ratio (mg/g). These samples will be used to assess the change in the urinary albumin:creatinine ratio throughout the trial. Samples should not be obtained if the subject is menstruating, has vigorously exercised within 24 hours, or had fever or an active infection within two days of the visit. Under such circumstances, the subject should provide a urine sample at an unscheduled visit.

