Two approaches will be used for handling data occurring after the initiation of glycemic rescue therapy. The first approach, which will be used for all safety endpoints in analyses of Phase A alone, will exclude all data following the initiation of rescue therapy at any timepoint, in order to avoid the confounding influence of the rescue therapy. The second approach, which will be used for all safety endpoints in analyses of Phase A alone and of Phases A+B combined, will include data following the initiation of rescue therapy. For analyses of Phase A alone, the "including rescue" approach will be considered primary for analyses of SAEs, discontinuations due to AEs, and ECGs, and the "excluding rescue" approach will be considered primary for all other endpoints. For analyses of hypoglycemia, the "excluding rescue" approach will be considered primary regardless of the time period being summarized. For analyses of Phase B alone, excluding/including rescue is not relevant, as there is no rescue therapy in Phase B.

Table 12 summarizes the analysis approaches for safety endpoints by study phase.

Study Phase(s)	Data Included	Endpoints	
A	Treatment Period data, ER	All safety endpoints	
	Treatment Period data, IR	All safety endpoints	
	All post-randomization data, IR	SAEs, Discontinuations due to AEs	
В	Treatment Period data	AEs, PDLCs	
A+B	Treatment Period data, IR	All safety endpoints	
	Treatment Period data, ER	Hypoglycemia	
	All post-randomization data, IR	SAEs, Discontinuations due to AEs	

Treatment Period includes up to 14 days post treatment for AEs, and up to 2 days post treatment for PDLCs.

ER = excluding data after initiation of glycemic rescue therapy

IR = including data after initiation of glycemic rescue therapy

The analysis of safety results will follow a tiered approach. The tiers differ with respect to the analyses that will be performed. Safety parameters or adverse events of special interest that are identified *a priori* constitute "Tier 1" safety endpoints that will be subject to inferential testing for statistical significance with p-values and 95% CIs provided for between-group comparisons. Between-group comparisons will be made between ertugliflozin and glimepiride. Other safety parameters will be considered Tier 2 or Tier 3. Tier 2 parameters will be assessed via point estimates with 95% CIs provided for between-group comparisons; only point estimates by treatment group are provided for Tier 3 safety parameters.

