**Protocol/Amendment No.:** 002-01

Adverse events (overall summary, specific terms, and system organ class terms) and predefined limits of change in laboratory parameters that are not pre- specified as Tier 1 endpoints will be classified as belonging to "Tier 2" or "Tier 3", based on the number of events observed. Membership in Tier 2 requires that at least 4 subjects in any treatment group exhibit the event or meet PDLC criterion; all other AEs and PDLCs will belong to Tier 3.

The threshold of at least 4 events was chosen because the 95% CI for the between-group difference in percent incidence will always include zero when treatment groups of equal size each have less than 4 events and thus would add little to the interpretation of potentially meaningful differences. Because many 95% CIs may be provided without adjustment for multiplicity, the CIs should be regarded as a helpful descriptive measure to be used in review, and not a formal method for assessing the statistical significance of the between-group differences in AEs and PDLCs.

Continuous measures such as changes from baseline in laboratory, ECG, and vital signs parameters will be considered Tier 3 safety parameters. Summary statistics for baseline, ontreatment, and change from baseline values will be provided by treatment group in table format. Mean change and percent change from baseline over time will be plotted with the corresponding standard errors. Any meaningful differences between these two approaches will be investigated further.

Percent change from baseline for all continuous endpoints in the lipid panel other than triglycerides will be analyzed using the cLDA method as described in Section 8.2.3.1. The cLDA model will include terms for treatment, time, and the interaction of time by treatment. Because the percent change in triglycerides typically has a skewed distribution, the cLDA model which is based on the symmetric normal distribution is not appropriate. Triglycerides will be analyzed using multiple imputation (MI) of missing values (if any) in conjunction with a robust regression (RREG) approach that uses M-estimation. A summary of the number (%) of subjects who initiate or have a change in lipid-lowering medication (new medication or new dose) will be provided. Based on this summary, additional analyses of lipid endpoints that censor data after initiation or changes in lipid-lowering medication may be performed.

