Table 13 summarizes the analysis strategy for safety endpoints. Adverse events associated with urinary tract infection, male and female genital mycotic infection, hypovolemia and symptomatic hypoglycemia AEs will be considered as prespecified safety parameters (Tier-1) for which p-values and 95% confidence intervals (CIs) for between-treatment differences will be provided using the Miettinen and Nurminen method [16].

Protocol/Amendment No.: 002-01

Table 13 Analysis Strategy for Safety Endpoints

Tier	Safety Endpoint	p- Value	95% CI for Treatment Comparison	Descriptive Statistics
Tier 1	AEs associated with urinary tract infection	X	X	X
	AEs associated with genital mycotic infection	X	X	X
	Any AE of symptomatic hypoglycemia	X	X	X
	AEs associated with hypovolemia	X	X	X
Tier 2 	Lipid Panel		X	X
	Triglycerides (TG)			
	LDL-C			
	HDL-C			
	Non-HDL-C			
	Total cholesterol			
	AE summary measures		X	X
	Specific AEs  , SOCs, and PDLC 		X	X
	AEs of documented hypoglycemia		X	X
	AEs of severe hypoglycemia		X	X
	Any			
	Requiring medical assistance			
	Not requiring medical assistance			
Tier 3	All endpoints listed under Tier 2 (above) that have			X
	incidence <4 subjects in all treatment groups			
	Additional hypoglycemia adverse event endpoints			X
	Change from baseline results (laboratory measurements,			X
	ECG, and vital signs)			

Non-continuous endpoints listed here will qualify for Tier 2 only if the incidence is ≥4 subjects in at least one of the treatment groups.

Among those endpoints not prespecified as Tier 1 endpoints.

SAE=Serious adverse event; SOC=System Organ Class; PDLC=Pre-Defined Limit of Change; X = results will be provided.

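### Under the general laboratory rule, urinary albumin:creatinine ratio would be plotted as mean percent change, which drifts upward in every arm from within-subject noise alone

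*Combined protocol and SAP*

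**What the plan says.** Section 7.1.2.1 states why ACR is collected: "These samples will be used to assess the change in the urinary albumin:creatinine ratio throughout the trial". The Trial Flow Chart (Section 6.0) schedules the urine collection at Visits 2 and 4, at Weeks 26, 52, 78 and 104, and at the rescue and discontinuation visits. Table 7 lists ACR among the laboratory evaluations.

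Section 8 does not name ACR, and the predefined limits of change in Section 12.6 contain no ACR criterion. What remains is the general rule in Section 8.2.3.2: "Continuous measures such as changes from baseline in laboratory, ECG, and vital signs parameters will be considered Tier 3 safety parameters". For these measures the tables are described only as follows: "Summary statistics for baseline, ontreatment, and change from baseline values will be provided by treatment group in table format". The plots are more specific: "Mean change and percent change from baseline over time will be plotted with the corresponding standard errors". Table 13 puts change-from-baseline results for laboratory measurements in Tier 3 with descriptive statistics only, and the text on tiers says that "only point estimates by treatment group are provided for Tier 3 safety parameters".

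Skewness is dealt with in the same section for one variable, triglycerides: "Because the percent change in triglycerides typically has a skewed distribution, the cLDA model which is based on the symmetric normal distribution is not appropriate". No log scale, geometric mean or median is named for ACR.

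**The concern.** ACR from a single urine sample is a ratio that varies multiplicatively within a subject. Section 7.1.2.1 itself treats it as easily disturbed, since it bars sampling during menstruation, after vigorous exercise, and around fever or infection. Percent change divides by one noisy baseline value. A baseline that is low by chance produces a very large percent increase, whereas one that is high by chance can never produce a fall of more than 100%. The errors do not balance, and the arm mean moves up.

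At stake is how the planned quantitative display of albuminuria reads. A plot with error bars clear of zero would suggest that albuminuria rose in all three arms when it had not. This matters because the change in ACR is the stated reason for taking the samples, and because these summaries are the only quantitative albuminuria result that the plan provides for.

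**Working it through.** The documents give no standard deviation, CV or expected change for ACR, so there is no figure of the plan's own to reproduce. The check asks what the planned statistics show when nothing has changed.

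**Inputs from the documents.** 410 subjects per arm and cumulative attrition of 0.312 at Week 52 (Section 8.2.6), so 410 × (1 − 0.312) = 282 per arm. That attrition was assumed for the A1C power calculation; here it only sizes the illustration.

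**Assumptions not in the documents.** ACR is log-normal; each subject has the same true level at baseline and follow-up; measurement errors at the two visits are independent with within-subject CV *c* from 20% to 100%; the median is 10 mg/g; the between-subject SD on the log scale is 1.0 or 1.3. The plotted percent change is taken to be the arm mean of individual percent changes.

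**Formula.** The within-subject variance on the log scale is w² = ln(1 + c²). The log ratio of follow-up to baseline has mean 0 and variance s² = 2w². Hence

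expected mean percent change = 100 × (exp(s²/2) − 1) = 100 × (exp(w²) − 1) = 100 × c².

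For c = 0.5 this is 100 × 0.25 = +25%. Stated through the SD of the log ratio, s = 0.6, 0.8 and 1.0 give +19.7%, +37.7% and +64.9%; these correspond to CVs of about 44%, 61% and 81%, inside the range below.

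**Simulation.** 4,000 replicates, 282 per arm, no true change, between-subject log-SD 1.0:

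| Within-subject CV | Formula | Simulated mean % change | Median SE (points) | Replicates with mean above +1.96 SE | Geometric mean ratio, % change |
|---|---|---|---|---|---|
| 20% | +4% | +4.0% | 1.8 | 62% | 0.00 |
| 30% | +9% | +9.1% | 2.8 | 91% | 0.10 |
| 50% | +25% | +24.9% | 5.5 | 99.9% | 0.03 |
| 70% | +49% | +49.2% | 9.4 | 100% | 0.23 |
| 100% | +100% | +100.0% | 18.2 | 100% | 0.25 |

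If the error bars were honest about a null effect, the fifth column would read about 2.5%. With between-subject log-SD 1.3 the simulated means are +3.9%, +9.0%, +25.1%, +48.8% and +99.6%. The shift therefore follows within-subject noise and not the spread of ACR between subjects.

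**The other statistics on the same data.**
- Arithmetic mean change stays centred on zero (−0.04 to +0.06 mg/g) and exceeds +1.96 SE in about 2% to 3% of replicates. Its median SE runs from 0.43 to 4.66 mg/g and grows with both sources of variability. It is imprecise but not shifted.
- Median percent change is within 0.5% of zero throughout.
- The difference between two arms of equal variability in mean percent change averages within 1 percentage point of zero.

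**The case against.** The strongest reply is that little hangs on this. ACR appears in no objective, has no predefined limit of change, and sits in Tier 3 without between-arm inference. Glimepiride would show the same drift, so the contrast between arms is roughly preserved. Renal safety rests on other things: the eGFR limits of change in Section 12.6 (falls above 30% and above 50%), the creatinine and eGFR discontinuation criteria in Section 5.8, blinded adjudication of renal failure in Section 7.3.4, and hypovolemia as a Tier 1 event. The renal concerns in Sections 4.1.2.2 and 7.3.4 are about volume depletion, eGFR and renal failure, not albuminuria. All of this stands and limits the point to presentation.

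The plan also leaves some room. Applying the rule to ACR is an inference, although no other rule covers it. The tabulated statistics are left open, so medians are not excluded. The sentence after the plotting rule promises to look into meaningful differences between two approaches, but it does not say which two. If it means absolute against percent change, the artefact might be noticed, but only after the plot exists. The plotting rule itself is explicit.

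Nor are triglycerides evidence of a contradiction. Section 8.2.3.2 drops a model for them because the lipid panel is Tier 2 with confidence intervals, whereas ACR has no planned model. The passage shows only that skewed percent change is recognised as a problem in this section.

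A reader might infer that the display could create a false difference between arms. That needs unequal within-subject variability: log-ratio SDs of 0.6 and 0.8 would give 37.7 − 19.7 = 18 points. Nothing in the documents suggests such a difference.

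**Conclusion.** The point holds for mean percent change in the by-arm ACR plot. If the plan's rule is followed, noise alone produces an apparent rise in every arm, with error bars that would often exclude zero. The expected size is 100 × CV²: +4% at a within-subject CV of 20%, up to +100% at a CV of 100%. Calling the shift large would go beyond the documents, because they do not give the CV; the result also rests on log-normality and independent errors at the two visits.

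Two further readings are not supported. A reader might take both planned curves to be biased upward, but arithmetic mean change is not. Its weakness is sensitivity to a few very high values, which Table 3 does nothing to limit because it sets no ACR bound at entry. A reader might also blame right skew between subjects, but the cause is within-subject variability in the baseline denominator.

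No hypothesis, power calculation or decision rule is affected. This is a free improvement.

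**What to change.** In Section 8.2.3.2, exempt ACR from the mean-change and percent-change plots. State that ACR will be analysed as the log of the ratio to baseline; that the back-transformed mean (the geometric mean ratio) with its 95% CI will be tabulated and plotted by arm and visit; and that medians and quartiles will be given in the table. The sentence should also say how albumin results below the assay's reporting limit enter the logarithm, since the documents give no rule.

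On the null data above, the geometric mean ratio stays within 0.3% of no change at every assumed CV. The interval is descriptive and within-arm, in place of the standard-error bars already planned, so ACR stays in Tier 3.

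The cost is one sentence and minor programming, with no new data. Section 8.2 allows non-confirmatory analyses to change after finalisation if the change and its reason are listed in the study report, so this does not need a protocol amendment of its own.

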## The following objectives will be assessed for ertugliflozin 15 mg q.d. and 5 mg q.d.

*In subjects with T2DM and inadequate glycemic control on metformin, after 52 weeks* 

(8) **Objective:** To assess the effect of the addition of ertugliflozin compared with the addition of glimepiride on change in fasting plasma glucose (FPG) from baseline.

- (9) **Objective:** To assess the effect of the addition of ertugliflozin compared with the addition of glimepiride on the proportion of subjects at the A1C goal of <7.0% (<53 mmol/mol).
- (10) **Objective:** To assess the effect of the addition of ertugliflozin compared with the addition of glimepiride on the proportion of subjects who require rescue and the time to rescue.
- (11) **Objective:** To assess the effect of the addition of ertugliflozin compared with the addition of glimepiride on diastolic blood pressure.
- (12) **Objective:** To assess the effect of the addition of ertugliflozin compared with the addition of glimepiride on durability of glycemic efficacy.
- (13) **Objective:** To assess the effect of the addition of ertugliflozin compared with the addition of glimepiride on the proportion of subjects meeting the composite endpoint of an A1C decrease >0.5% with no symptomatic hypoglycemia and no body weight gain.
- (14) **Objective:** To assess the effect of the addition of ertugliflozin compared with the addition of glimepiride on the proportion of subjects meeting the composite endpoint of an A1C <7.0% with no symptomatic hypoglycemia
- (15) **Objective:** To assess the effect of the addition of ertugliflozin compared with the addition of glimepiride on lipid profile (including HDL-C, triglycerides, total cholesterol, LDL-C, and non-HDL-C cholesterol).
- (16) **Objective:** To assess the effect of the addition of ertugliflozin compared with the addition of glimepiride on HOMA-%β.

In subjects with T2DM and inadequate glycemic control on metformin, after 104 weeks

- (17) **Objective:** To assess the effects of the addition of ertugliflozin compared with the addition of glimepiride on A1C, FPG, and the proportion of subjects at the A1C goal of <7.0% (<53 mmol/mol).
- (18) **Objective:** To assess the effects of the addition of ertugliflozin compared with the addition of glimepiride on symptomatic hypoglycemia.
- (19) **Objective:** To assess the effects of the addition of ertugliflozin compared with the addition of glimepiride on change in body weight from baseline.

04T4BY

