# **8.2.3.1** Statistical Methods for Efficacy Analyses

# Phase A (Week 0 to Week 52)

The primary efficacy analyses will compare the efficacy of ertugliflozin relative to glimepiride in change from baseline in A1C at Week 52. The mean change from baseline in A1C at Week 52 in the ertugliflozin 15 mg group will be compared to that in the glimepiride group using the estimated treatment difference via a constrained longitudinal data analysis (cLDA) model, proposed by Liang and Zeger [15]. This cLDA model assumes a common mean across treatment groups at baseline and a different mean for each treatment at each of the post-baseline time points. In this model, the response vector consists of baseline values and the values observed at each post-baseline time point. The cLDA model will include terms for treatment, time, prior antihyperglycemic medication (monotherapy or dual therapy), baseline eGFR, and the interaction of time by treatment. Time will be treated as a categorical variable so that no restriction is imposed on the trajectory of the means over time. The treatment difference in terms of mean change from baseline to a given time point will be estimated and tested from this model. Ertugliflozin 15 mg will be declared non-inferior to glimepiride in terms of A1C reduction if the upper limit of the two-sided 95% confidence interval (CI) for the mean difference between ertugliflozin 15 mg and glimepiride at Week 52 is less than the non-inferiority margin,  $\delta$ =0.3%. This margin was chosen because changes from baseline smaller than -0.3% have limited clinical impact, and the 0.3% margin balances lesser clinical impact with a study sample size that is feasible to conduct. The non-inferiority test for ertugliflozin 5 mg in A1C reduction will use the same approach described above following the multiplicity control strategy in Section 8.2.5. If non-inferiority is declared for ertugliflozin 15 mg, then an assessment of superiority will be conducted following the multiplicity control strategy described in Section 8.2.5. For the cLDA model, the Kenward-Roger adjustment will be used with restricted (or residual) maximum likelihood (REML) to make proper statistical inference. An unstructured covariance matrix will be used to model the correlation among repeated measurements and hence avoids the potential bias that could result from the use of specific structured covariance models. If the unstructured covariance model fails to converge with the default Newton-Raphson algorithm, the Fisher scoring algorithm or other appropriate methods can be used to provide initial values of the covariance parameters. In the rare event that none of the above methods yield convergence, a structured covariance such as Toeplitz can be used to model the correlation among repeated measurements. In this case, the empirical option will be used because the sandwich variance estimator is asymptotically unbiased while the model-based variance estimator can substantially overestimate or underestimate the true variance. The cLDA model uses the maximum likelihood principle to estimate the parameters and account for missing data in an implicit fashion. Values of eGFR that are >120 mL/min/1.73 m^2 will be set to 120  $mL/min/1.73 m^2$ .

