
**Protocol/Amendment No.:** 002-01

Although the baseline measurement is included in the response vector, it is independent of treatment, and hence, the baseline means are constrained to be the same for different treatment groups. Of note, in the event that there are no missing data, the estimated treatment difference from the above cLDA model will be identical to that from a traditional longitudinal analysis of covariance (ANCOVA) model which uses the baseline value as a covariate. However, unlike longitudinal ANCOVA, the cLDA model accounts for variability in the baseline values, thus providing more accurate standard errors and CIs for individual treatment effects. Moreover, this model allows the inclusion of subjects who are missing either the baseline or post-baseline measurements, thereby increasing efficiency. An example of SAS implementation code is given in Section 12.8.

All other continuous efficacy endpoints will be analyzed using the above cLDA method described for A1C

An analysis of covariance (ANCOVA) model will be used in the PP population as sensitivity analyses for the primary and key secondary efficacy endpoints at Week 52. The ANCOVA model will include treatment, prior antihyperglycemic medication, baseline eGFR, and baseline value. By definition, there will be no missing outcome data in the PP population.

The ANCOVA model as described above will also be used in the FAS population for the primary and key secondary efficacy endpoints. The last-observation-carried-forward (LOCF) method will be used to impute missing data.

If the size of the mFAS population (described in Section 8.2.2.1) differs from the size of the FAS by >2% in any treatment group, primary and key secondary endpoints will be analyzed in the mFAS population using the same cLDA methodology described for the FAS.

All continuous efficacy endpoints will be summarized and plotted over time by treatment group.

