# 8.2.7 Subgroup Analyses and Effect of Baseline Factors

To assess whether the treatment effect at Week 52 is consistent across various subgroups, the estimate of the between-group treatment effect (with a nominal 95% CI) for the primary endpoint will be estimated and plotted within each category of the following classification variables:

- Baseline A1C levels: by categories: <8.0%; ≥8.0%
- Age categories:  $\leq$  or > median age
- Gender (female; male)
- Race (White, Black, Asian, Other)
- Ethnicity (Hispanic or Latino, Not Hispanic or Latino)
- BMI ( $\leq$  or > median)
- Prior antihyperglycemic therapy (monotherapy or dual therapy)
- Time since diagnosis of Diabetes ( $\leq$  or > median years)

For the subgroups that have only 2 categories, if the sample size is not at least 20 subjects in all of the treatment groups in each subgroup category, then that subgroup analysis will not be performed. For the race subgroup analysis, if the sample size is not at least 20 subjects in all of the treatment groups in a certain race category, then that race will be combined with the "Other" race category. The consistency of the treatment effect will be assessed in the context of a repeated measures ANCOVA (RMANCOVA) method, which is a generalization of the standard ANCOVA to accommodate repeated measurements. The RMANCOVA model will adjust for baseline value for A1C, treatment, baseline eGFR, subgroup, and treatment-bysubgroup interaction. Time is treated as a categorical variable and time-specific versions of each term listed above at each week will be used to acknowledge the repeated nature of the measurements. An unstructured covariance matrix will be used to model the correlation among repeated measurements. For subgroup analyses based on factors that are already in the main model, the respective term will appear in the model only once. Treatment effects and nominal 95% confidence intervals by category for the classification variables listed above will be reported as well as presented graphically. Formal statistical testing of treatment-by-subgroup interactions will not be performed.

**Protocol/Amendment No.:** 002-01

The treatment effect across trial centers will be summarized for A1C at Week 52 with descriptive statistics.

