#### 12.8 SAS Code for cLDA Model

Sample SAS code for fitting cLDA model are provided below. This serves as an example only, not the actual implementation codes for this trial. The sample code below assumes that there is a baseline and 4 post-baseline measurements (Weeks 6, 12, 18 and 26) and 2 treatment groups (MK-8835 and placebo).

```
*******************************
** data step necessary prior to running SAS PROC MIXED;
*******************************
DATA long; SET long;
ARRAY T{5} t0-t4; * time indicator variables;
ARRAY TT{5} tt0-tt4; * time by treatment indicator variables;
** define week times treatment indicator variables:
DO i = 1 TO 5;
t\{i\} = (time=(i-1));
tt\{i\} = t\{i\}*(trt=1);
END;
DROP i;
RUN:
*************************
** fitting the cLDA model using SAS PROC MIXED;
********************
PROC MIXED DATA=long;
CLASS subj time; ** subj is the subject id number **;
MODEL y=time tt1 tt2 tt3 tt4;
REPEATED time / SUBJECT=subj TYPE=UN;
ESTIMATE 'T1 Diff (MK-8835-Placebo)' tt1 1;
ESTIMATE 'T2 Diff (MK-8835-Placebo)' tt2 1;
ESTIMATE 'T3 Diff (MK-8835-Placebo)' tt3 1;
ESTIMATE 'T4 Diff (MK-8835-Placebo)' tt4 1;
ESTIMATE 'T1 Placebo LSM' time -1 1 0 0 0;
ESTIMATE 'T2 Placebo LSM' time -1 0 1 0 0:
ESTIMATE 'T3 Placebo LSM' time -1 0 0 1 0;
ESTIMATE 'T4 Placebo LSM' time -1 0 0 0 1;
ESTIMATE 'T1 MK-8835LSM' time -1 1 0 0 0 tt1 1;
ESTIMATE 'T2 MK-8835LSM' time -1 0 1 0 0 tt2 1;
ESTIMATE 'T3 MK-8835LSM' time -1 0 0 1 0 tt3 1;
ESTIMATE 'T4 MK-8835LSM' time -1 0 0 0 1 tt4 1;
ODS OUTPUT Estimates=outm1;
RUN;
```

Protocol/Amendment No.: 002-01

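### Does the lipid percent-change cLDA fail because the plan does not say what stands at Week 0?

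*Combined protocol and SAP*

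**What the plan says.** The lipid profile is secondary objective 15 in Section 3.2: "To assess the effect of the addition of ertugliflozin compared with the addition of glimepiride on lipid profile". The objective has no hypothesis attached. Table 13 places the lipid panel in Tier 2, with a 95% CI and no p-value.

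Section 8.2.3.2 assigns the method, by reference to Section 8.2.3.1: "Percent change from baseline for all continuous endpoints in the lipid panel other than triglycerides will be analyzed using the cLDA method". It then lists the terms: "The cLDA model will include terms for treatment, time, and the interaction of time by treatment". Triglycerides are treated separately, for this reason: "Because the percent change in triglycerides typically has a skewed distribution". Percent change itself is therefore the modelled quantity after baseline.

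The cited method, in Section 8.2.3.1, defines the vector: "In this model, the response vector consists of baseline values and the values observed at each post-baseline time point". It adds: "Although the baseline measurement is included in the response vector, it is independent of treatment". It constrains the baseline means to be equal across arms, uses an unstructured covariance, and is said to account for variability in the baseline values.

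Section 12.7 lists Weeks 26, 52 and 104 as the only post-randomization lipid time points. Section 8.2 says that no separate SAP will be issued. It also says that changes to non-confirmatory analyses will be listed and explained in the CSR.

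**The concern.** A cLDA takes its baseline adjustment from the baseline element of the response vector and needs no baseline covariate. The lipid model lists no baseline lipid term, so whatever stands at Week 0 is its only route to adjustment.

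For A1C this causes no difficulty, because absolute change is a linear contrast of values on one scale. Percent change is not a linear contrast of raw values, so the A1C description does not carry over word for word. If percent change is put at every time point, Week 0 is 0 for every subject and the unstructured covariance is singular. If the analyst drops Week 0 so that the model runs, the comparison is unadjusted.

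At stake is the precision of the lipid intervals, and whether two analysts would fit the same model from the same sentence. The A1C, body weight and blood pressure analyses are not involved.

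**Working it through.** **1. The plan's own cLDA figure.** Only the A1C design is quantified (Section 8.2.6): 337 effective subjects per arm, SD 1.0%, margin 0.3%, 97% power, half-width 0.15%.

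- SE of the difference = 1.0 × √(2/337) = 0.07704
- Half-width = 1.96 × 0.07704 = 0.151
- Power = Φ(0.3/0.07704 − 1.96) = Φ(1.934) = 0.9735
- Effective N from the stated attrition and correlation matrix = 337.4

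All reproduce. No figure is stated for lipids.

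**2. Three readings of Week 0, set against Section 8.2.3.1.**

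| Week 0 element | Can it be fitted? | Does it match the cited method? |
|---|---|---|
| Percent change (0 for all) | No: 3 × 3 covariance (Weeks 0, 26, 52) has a zero row and column, determinant 0, rank 2 | No: no baseline variability and no baseline mean to constrain |
| Omitted | Yes | No: the vector must contain baseline values |
| Baseline lipid value | Yes: rank 3 | Yes |

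The A1C endpoint is a precedent. It is named as change from baseline, which is also 0 at baseline for everyone, yet the A1C vector holds the baseline value. Naming a change endpoint does not, in this plan, put zeros at Week 0.

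**3. What the matching reading estimates.** Let b be the baseline lipid value with common mean μ₀ and variance σ₀², and let p be percent change at visit t, with covariance σ₀ₜ with b. Then

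E(p | b, arm) = mean at t for that arm + (σ₀ₜ/σ₀²)(b − μ₀).

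This is an ANCOVA of percent change on baseline. A numerical check used complete data, 2 arms of 410, and assumed log-normal lipids with mean 100, CV 30% and correlation 0.4, 0.6 or 0.8. The Week 52 differences from the cLDA were −2.4490, −1.1751 and −2.9044. The ANCOVA gave the same values to four decimals.

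**4. Cost if an analyst omitted Week 0.** The simulation used 3 arms of 410 and Weeks 26 and 52, with the plan's attrition for those weeks (16.0% and 31.2%, Section 8.2.6) and 300 runs per setting. Assumed, because the documents give no lipid variability: baseline mean 95 mg/dL, CV 32%, true effect 5%, correlation 0.5 to 0.8.

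| Within-subject correlation | SE, baseline at Week 0 | SE, Week 0 omitted | Ratio |
|---|---|---|---|
| 0.5 | 2.516 | 2.812 | 1.118 |
| 0.6 | 2.264 | 2.473 | 1.092 |
| 0.7 | 1.977 | 2.111 | 1.068 |
| 0.8 | 1.629 | 1.703 | 1.045 |

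Intervals are therefore 5% to 12% wider. A check with complete data uses ratio = 1/√(1 − r²), where r is the correlation of baseline with Week 52 percent change. At correlation 0.5, r = −0.46 and the ratio is 1/√(1 − 0.2116) = 1.126. At correlation 0.8, r = −0.30 and it is 1/√(1 − 0.09) = 1.048. Both are close to the simulated values. A wider log-normal grid (CV 20% to 35%, correlation 0.9 to 0.4) gives 2% to 18%.

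**5. Bias.** In 2,000 simulated null trials at CV 30%, the mean difference was within 0.05 percentage points of 0 with and without baseline. In the step 4 simulation, a chance baseline imbalance of 1 mg/dL moved the unadjusted estimate by about −0.5 to −0.2 percentage points (correlation 0.5 to 0.8). That is random error and already counts in the wider interval.

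**6. The sample code.** A within-arm contrast such as "ESTIMATE 'T1 Placebo LSM' time -1 1 0 0 0" would make no sense for a vector of a lipid value followed by percentages. Section 12.8 presents the code as an example only, with two arms, a placebo and visits ending at Week 26. The time-by-treatment coefficients, which carry the treatment comparison, are not affected.

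**The case for a change.** The best case for a change is that the baseline sentence in Section 8.2.3.1 was written for A1C, where baseline and follow-up share one unit. It permits a vector of a lipid value followed by percentages but does not select it, and mixing units is unusual enough that some analysts would hesitate. With no separate SAP, the detail has no other stated home. For a Tier 2 endpoint the estimate and interval are the whole between-group result, and one sentence would settle the matter at no cost.

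It is true that Section 8.2.3.2 does not state the Week 0 element, and a clarifying sentence would do no harm. The danger does not follow. A zero Week 0 does not run, so it cannot produce a wrong answer unnoticed. Omitting Week 0 departs from the method that the section cites, so it is not an equally valid reading of the text. An analyst uneasy about mixed units has an alternative of a type the plan already uses. Section 8.2.7 describes a repeated-measures ANCOVA for A1C subgroups: "The RMANCOVA model will adjust for baseline value for A1C, treatment, baseline eGFR, subgroup". A model of that kind, with baseline lipid as the covariate, gives the same treatment difference as the matching cLDA when data are complete. The sensible routes therefore agree.

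**Conclusion.** The concern identifies a missing detail and not a flaw in the analysis. Read together, Sections 8.2.3.2 and 8.2.3.1 lead to the baseline lipid value at Week 0 with a common mean across arms, and percent change at each later visit. That model can be fitted and is baseline-adjusted. The within-group mean percent change is then simply the model mean at the visit.

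A loss arises only if an analyst departs from the cited method by dropping the baseline row. The comparison then stays unbiased, with intervals about 5% to 12% wider. That range rests on assumed lipid variability (CV 32%, within-subject correlation 0.8 to 0.5) and the plan's attrition rates. It touches only a Tier 2 safety summary with no p-value and no hypothesis, outside the multiplicity scheme. Writing the Week 0 element down would record what a competent analyst does anyway, and the CSR can state it. No change to the plan follows.
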